8.2.6.2 Safety Measures

In addition to the measures described under efficacy, including CSSR-S, BISS (MADRS) CHRT-SR and CHRT-C and SIBQ, the following safety measures will be employed:

Patient Rated Inventory of Side Effects (PRISE): The self-reported PRISE questionnaire will be used for the specific symptoms considered by the patients as more or less tolerable drug side effects. The nine domains (gastrointestinal, heart, skin, nervous system, genital/urinary, sleep, sexual functioning, and other symptoms) will be individually and cumulatively evaluated using a paired t-test with each study group and an unpaired t-test for K/N vs. K/L and K/P to assess the mean side effect or adverse event. Reasons for premature discontinuation and dose reduction, including intolerable side effects, will be recorded. Drug interactions between DCS and lurasidone will be examined.

Clinician-Administered Dissociative States Scale (CADSS): The CADSS is a 23-item scale (Bremner et al 1998). It is a reliable, valid instrument. The severity of each dissociative symptom ranges from 0 (not present) to 4 (extreme). The CADSS total score will be calculated as the sum of the individual item scores. For the CADSS, change from the first time point to each subsequent time point will be calculated as the 40-minute, 80-minute, and 120-minute assessment minus the 0 (-5 minutes) score. The scale is administered at 0 (-5 minutes), 40, 80, and 120 minutes from the start of the infusion. The timeframe is “at this moment”. The CADSS has been validated in healthy subjects and patients with psychiatric illness.

Barnes Akathisia Scale (BARS): The Barnes Akathisia Scale (Barnes TR, 1989) is a clinician-rated scale to assess drug-induced akathisia and classify it as absent, mild, moderate, or severe. It comprises items for rating the observable, restless movements which characterize the condition, the subjective awareness of restlessness, and any distress associated with the akathisia. In addition, there is an item for rating global severity. It is the scale used most commonly in trials comparing incidence and severity of akathisia between antipsychotic medications and placebo. The time frame is “at this time”. With trained raters, the BARS has demonstrated strong inter-rater reliability (Kappa= 0.74-0.95) (Barnes , 2003). The BARS has been used to support the concurrent validity of actigraphic monitoring in akathisia (Barnes, 2003).

8.2.6.3 Other Diagnostic Instruments

MINI 7.0.2: The M.I.N.I. International Neuropsychiatric Interview (M.I.N.I.) is a short, structured diagnostic interview developed initially in 1990 by psychiatrists and clinicians in the United States and Europe for DSM-III-R and ICD-10 psychiatric disorders. The tool has been updated to map to DSM-5 diagnostic criteria in the MINI 7.0.2.

8.2.7 Reliability Training

All clinicians chosen to be involved in the assessment of study subjects are experienced using standardized clinician-rated measures. They will have all received extensive training in the use of these instruments in coordination with MGH CTNI. Raters will be certified in the use of the C-SSRS and the BISS prior to participation in the study.

8.2.8 Subject Adherence to Protocol

Every effort will be made to encourage subjects to comply with the procedures and the assessments involved in study. Subjects will be compensated for their time at each visit, at a rate determined appropriate by the sponsor and the IRB (estimated compensation: \$20/hour). We believe that this level of subject compensation, while non-coercive, facilitates adherence to assessments and procedures that require frequent, inconvenient visits.

Table 5 Protocol Violation Definitions

	Major Protocol Violation	Minor Protocol Violation
The list of examples is intended as a guide and is not all-inclusive.		
Definition	A violation that may : 
 • Impact subject safety, • Affect the integrity of study data, and/ or • Affect the subject's willingness to participate in the study, and/or • Introduce bias. 	A violation that does not : 
 • Impact subject safety, • Compromise the integrity of study data, and/ or • Affect the subject's willingness to participate in the study, and/or • Introduce bias.
Examples (not all-inclusive)	
 • Failure to obtain informed consent • Informed consent obtained by an unauthorized individual • Enrollment of a subject who did not meet eligibility criteria for whom a protocol exception was not obtained • Performing a study procedure that is not approved by the IRB and/or is not in the protocol • Failure to perform a required lab test that, in the opinion of the Site Investigator, may affect subject safety or data integrity • Failure to perform or follow a study procedure that, in the opinion of the Site Investigator, may affect subject safety or data integrity • Failure to follow safety (AE) management plan • Failure to report a SAE to the IRB and/or Coordination Center 	
 • Implementation of unapproved recruitment procedures • Only a photocopy of the signed/ dated consent form is available (the original is missing) • Pages are missing from the signed/ dated informed consent form • Use of invalid consent form (i.e., without IRB approval or outdated/expired form) • Failure to perform or follow an approved study procedure that, in the opinion of the Site Investigator, does not affect subject safety or data integrity • Study procedure conducted out of sequence • Failure to perform a required lab test • Missing lab results • Study Visit out of approved window • Over-enrollment • Enrollment of subjects after IRB approval of the study has expired • Failure to submit a continuing review application to the IRB before study expiration
Reporting Requirements	
 • Record the date discovered, date occurred, description of event in the Protocol Deviation Log. • Notify the Coordinating Center within 24 business hours. 	
 • Record the date discovered, date occurred, description of event in the Protocol Deviation Log. • Notify the Coordinating Center

A Relapse Adjudication Committee (RAC) will be assembled and managed by MGH CTNI. All site-reported relapse events will be reviewed by the RAC, and a determination made as to whether the event met study criteria for relapse. The results of each adjudication will be entered into the study database. The RAC will meet monthly to adjudicate the events.

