6.4 Study Population

The study analyses will be conducted in a GCP environment (ICH E6). All analyses will be pre-specified in a Statistical Analysis Plan (SAP) prior to beginning subject enrollment. The study will have prospectively defined study populations including separate evaluability rules for the ketamine treatment (Stage 1) and randomized treatment (Stage 2).

For Stage 1, the Intent-to-Treat (ITT) population will include all subjects who received the ketamine infusion and have the 24-hour post-infusion efficacy assessments. The Per-Protocol Population will include the subset of ITT subjects who were eligible, who had the 24-hour post-infusion efficacy assessments within 18 to 30 hours post the start of the initial infusion, and who had no major protocol violations. The Safety Population will include all subjects treated with ketamine who have any post-baseline safety data.

For Stage 2, the ITT population will include all subjects who received the randomized study treatment and have any post-baseline efficacy assessments. The Per-Protocol population will include the subset of ITT subjects who were eligible, who have any post-baseline efficacy assessments within 1 day of scheduled visits through Day 7 and within 2 days of scheduled visits through Day 42, and who had no major protocol violations. The Safety Population will include all subjects as treated with study treatment who have any post-baseline safety data through Day 70.

The ITT population will be used for the primary analyses. If <5% are to be excluded from the ITT population, then the analysis will not be performed for the PP population.

Every effort will be made to encourage subjects to comply with the procedures and the assessments involved in study. Non-compliance will be tracked. Protocol violations will be reviewed in real time; rules will be set for exclusions from the PP population.

A sufficient number (estimated to be 192 subjects) will be entered into Stage 1 in order to have 124 randomized subjects to complete Stage 2. IRB-approved written informed consent will be obtained from all subjects before any protocol-specified procedures are carried out. The subjects will be drawn from a sample of subjects with BD with suicidal ideation, diagnosed with the use of the MINI 7.0.2 for DSM 5. For entry into the study, all inclusion criteria must be met, and none of the exclusion criteria can be met.

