7. SELECTION AND WITHDRAWAL OF SUBJECTS

Subjects must meet all of the inclusion and none of the exclusion criteria to be qualified to participate in this study.

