7.3 Selection and Withdrawal of Subjects

Eligibility criteria for this study have been carefully considered to ensure the safety of the study subjects and to ensure that the results of the study are meaningful in relation to the research hypotheses. It is imperative that subjects fully meet all eligibility criteria.

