13.3 Study Populations

The study will have prospectively defined study populations including separate evaluability rules for the Ketamine treatment (Stage 1) and randomized treatment (Stage 2).

For Stage 1, the Intent-to-Treat population will include all subjects who received the Ketamine infusion and they have the 24 hours post-infusion efficacy assessments. The Per-Protocol population will include the subset of ITT subjects who were eligible, who had the 24 hour post-infusion efficacy assessments within 18 to 30 hours post the start of the initial infusion, and who had no major protocol violations. The Safety Population will include all subjects treated with Ketamine and with any post-baseline safety data.

For Stage 2, the Intent-to-Treat population will include all subjects who received the randomized study treatment and have any post-baseline efficacy assessments. The Per-Protocol population will include the subset of ITT subjects who were eligible, who have any post-baseline efficacy assessments within 1 day of scheduled visits through Day 7 and within 3 days of scheduled visits through Day 42, and who had no major protocol violations. The Safety Population will include all subjects as treated with study treatment and with any post-baseline safety data.

The ITT population will be used for the primary analyses. If <5% are to be excluded from the ITT population, then the analysis will not be performed for the PP population.

Every effort will be made to encourage patients to comply with the procedures and the assessments involved in study. Non-compliance will be tracked. Protocol violations will be reviewed in real time; prospective rules will be set for exclusions from the PP population.

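### Table 5 implies an eligibility waiver that the rest of the protocol does not allow, and rates an unapproved consent form and enrolment after IRB expiry as minor against its own definition

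*Combined protocol and SAP*

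**What the plan says.** **Eligibility.** Section 7 opens with "Subjects must meet all of the inclusion and none of the exclusion criteria to be qualified to participate in this study". Section 7.3 adds "It is imperative that subjects fully meet all eligibility criteria", and Section 6.4 says "For entry into the study, all inclusion criteria must be met, and none of the exclusion criteria can be met". Section 8.1.4 repeats the rule, with emphasis, at the point of ketamine infusion. Table 5 then gives, as one example of a major violation, "Enrollment of a subject who did not meet eligibility criteria for whom a protocol exception was not obtained".

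**Consent and IRB approval.** The minor column of Table 5 includes "Use of invalid consent form (i.e., without IRB approval or outdated/expired form)" and "Enrollment of subjects after IRB approval of the study has expired". The major column includes failure to obtain consent at all and "Performing a study procedure that is not approved by the IRB"; that last entry goes on to cover procedures absent from the protocol. The definition row separates the columns by effect. A violation is major if it may affect safety, data integrity or willingness to participate, or may introduce bias. It is minor only if it does none of these. Section 14.3 requires IRB approval before screening and enrolment, and written, dated approval of the consent form before the study starts.

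**Where the label is used.** Sections 6.4 and 13.3 define the Stage 2 per-protocol (PP) set as ITT subjects who were eligible, had assessments within the visit windows, and had no major violation. Section 13.3 also states: "If <5% are to be excluded from the ITT population, then the analysis will not be performed for the PP population".

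**The concern.** A site reading Table 5 could reasonably conclude that an ineligible subject may be enrolled if someone agrees to an exception, and that such an enrolment need not be logged as major. The eligibility sections say the opposite. The population is acutely suicidal and the first study act is an open-label ketamine infusion, so an undefined waiver route is a matter of subject protection.

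The consent and IRB items raise a related problem. Enrolling someone on a form the IRB has not approved, or after its approval has lapsed, is classed with missing lab results and out-of-window visits. The minor label keeps these events out of the category that must be notified within 24 business hours, and it keeps the subjects in the PP set.

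**Working it through.** No arithmetic applies. The check sets the texts side by side.

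**1. Is there a waiver route?**

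- Sections 6.4, 7, 7.3 and 8.1.4 each require full eligibility, and none provides an exception.
- Table 5 makes ineligible enrolment major on condition that no exception was obtained. The condition has meaning only if exceptions can be obtained.
- No section says who grants one, on what grounds, or how the subject is then analysed. Section 14.2 has the Medical Monitor approve the eligibility of each screened subject but gives no power to set criteria aside.
- The only other use of the term is in Section 9.2, which applies it to subjects above a stated lurasidone dose at baseline. That is one named case, not a general process. It also sits beside text in the same section and in Section 4.6 on stopping or excluding prior lurasidone, and these passages must be reconciled.

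Table 5 therefore implies a route that four sections do not allow and that none defines.

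**2. Do the two minor items fit the minor definition?**

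- *Invalid consent form.* An unapproved or outdated form may lack current risk information, so it may affect willingness to participate. The major test needs only that possibility. Section 14.3 requires IRB approval of the form, and Section 16.3 requires the form to carry the elements the IRB demands.
- *Enrolment after IRB expiry.* The subject is enrolled and infused without approval in force, so an effect on safety cannot be ruled out. Section 14.3 does not mention lapse in words, but enrolling after expiry is enrolling without the approval it requires.

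Both items meet the major definition and neither can be shown to meet the minor one.

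**3. What does the label change?**

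- *ITT set.* Stage 2 ITT membership depends on receiving randomised treatment and having a post-baseline efficacy assessment. Violation status plays no part, so the primary analysis is unaffected by the labels.
- *PP set, waived subjects.* They did not meet the criteria, so on the ordinary reading they fail the eligibility condition whatever Table 5 calls them.
- *PP set, consent and IRB items.* Nothing else in the definition removes these subjects. As minor violations they stay in; as major violations they leave.

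**The case against.** The strongest reply is that Table 5 only classifies violations. It grants no waiver in words, does not list an excepted enrolment as minor, and describes its examples as a guide that is not exhaustive. Independent raters confirm diagnosis, C-SSRS and BISS (Section 8.1.3), and the Medical Monitor approves eligibility (Section 14.2). Section 13.3 promises further prospective rules for PP exclusions, so Table 5 is not the only determinant. Removing subjects from PP for a form-version or IRB defect is partly an administrative choice, since neither defect changes the treatment received or how outcomes are measured.

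Much of this stands, and it limits the consequences. It does not remove an explicit minor label that contradicts the definition in the same table, or explain a qualifier that refers to a process found nowhere.

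A reader might infer more than the documents support:

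- *That waivers weaken the primary endpoint.* This assumes severity criteria would be the ones waived, and nothing says so. Response needs both a MADRS reduction of at least 25% and C-SSRS of 3 or less, so meeting one leg unchanged does not make a responder. Relapse can also be reached through C-SSRS or a change of treatment plan.
- *That one subject's label decides whether the PP analysis is run.* Five per cent of the 124 randomised is 6.2, which suggests a switch between 6 and 7 exclusions. The rule, however, is based on the ITT set, whose size is not known in advance; at 120, six exclusions are already 6/120 = 5.0%. Waived subjects would count as exclusions under either label.
- *That the number affected can be estimated.* The documents give no waiver rate.
- *That enrolment after expiry is listed in both columns.* The major entry on unapproved procedures most naturally describes the procedure itself, and lapsed approval has its own entry. The point does not rest on a double listing.
- *That minor violations carry no reporting deadline.* Both columns require notification. The minor cell appears to break off in the available text, so its time limit may simply be missing there.

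**Conclusion.** The conflict is real in both places and nothing elsewhere in the protocol resolves it. Its reach is limited to three things: subject protection, because an undefined waiver route leads to ketamine infusion; escalation of consent and IRB failures; and PP membership for subjects with those failures. The number of subjects cannot be stated.

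The conclusion rests on reading the exception clause as implying that exceptions exist, and on reading the PP eligibility condition in its ordinary sense. If the sponsor intended a waived subject to count as eligible, waived subjects would also enter the PP set, and the plan would need to say so. The correction is worth making because the present wording could change what sites do, but it is not a threat to the primary result.

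**What to change.** - In Table 5, delete the qualifier about a protocol exception, so that every ineligible enrolment is a major violation.
- In Section 7.3, state that eligibility waivers are not granted.
- Reconcile that statement with the exception named in Section 9.2, so that no reference to an undefined exception remains. How prior lurasidone is handled is for the sponsor to settle.
- Move the use of an invalid consent form and enrolment after IRB expiry to the major column. Under the existing PP rule those subjects then leave the PP set, with no further change to Sections 6.4 or 13.3.

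The cost is a wording change in Table 5 and Sections 7.3 and 9.2. A few borderline subjects could not be enrolled, and the count of major violations might be slightly higher. The endpoint, sample size and primary analysis are unchanged.

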9. TREATMENT OF SUBJECTS

9.1 Investigational Drug Dose and Administration

In our planned study, physicians will have the ability to increase the lurasidone at any point after the initial titration period for control of agitation, or decrease both the DCS and lurasidone dose according to the titration table below, in response to somnolence or extrapyramidal side effects. This titration will be effected while maintaining a blinded study design. The titration strategy is outlined in Table 6.

Table 6 Dose Titration

Day	AM dose		PM dose		Total Daily dose	
	DCS	Lurasidone	DCS	Lurasidone	DCS	Lurasidone
1	350	16.5	0	16.5	350	33
2	475	16.5	0	16.5	475	33
3	350	16.5	350	33	700	49.5
4	350	16.5	475	33	825	49.5
5	475	33	475	33	950	66
Uptitration for Agitation						
step 1	475	33	475	66	950	99
step 2	475	66	475	66	950	132
Stepdown for Somnolence						
step 1	350	16.5	475	33	825	49.5
step 2	350	16.5	350	16.5	700	33
Preferred dose	475	33	475	33	950	66

9.3 Randomization/Method of Assigning Subjects to Treatment

Following the documented observance of a therapeutic response to intravenous ketamine as defined by a 25% or greater reduction in the MADRS score and a score of ≤ 3 on the C-SSRS, at 24 hours post infusion, patients will be randomized 2:1:1 to either a fixed dose combination of DCS + lurasidone (NRX-101), to an identical capsule containing placebo+lurasidone, or to an identical capsule containing placebo. Site blocking will be used to ensure that treatment and control groups are balanced per site.

9.4 Blinding

The investigator, subject, and study staff will be blinded. Packaging and labeling of the study drugs will be performed in a way to ensure blinding throughout the study.

No member of the study team at study sites nor the CRO (the group responsible for study data management and site monitoring) will have access to the randomization scheme during the conduct of the study with the exception of the group responsible for maintaining the IWRS. That group will be able to identify patient-specific treatment according to the uniquely assigned kit number.

The unblinding of specific kits will be performed by the sponsor's Chief Medical Officer.

No treatment groups or kits will be otherwise unblinded after database lock.

Breaking the blind in a clinical trial on an emergency basis by the site should only occur when knowledge of the treatment to which a subject was allocated would have implications for the medical management of the subject in case of a Serious Adverse Event (SAE). However, subjects that relapse or experience a SAE will require real-time interaction with the medical monitor to confirm the event and to decide if the event must be reported to regulatory agencies or IRBs.

The Data Safety and Monitoring Board (DSMB) (refer to Section 14.2) can request a code break, either for an individual subject or on a group basis as described in the DSMB charter. The DSMB may request to break the blind if:

- There is an imbalance in safety parameters between groups and/or
- In case of single or multiple significant AEs/SAEs that might be drug-related.

In such a case, the chair of the DSMB would request unblinding, either of an individual subject or on a group basis, and the CRO would then request unblinding from the third party keeper of the randomization codes.

9.5 Dose Adjustment and Stopping Rules

Subjects will be allowed to titrate up or down, as outlined above, in the event of intolerable side effects. No other dose modifications will be allowed.

Every effort will be made to keep the subject in the study for the full study period consisting of 7 days of acute treatment plus 6 weekly follow-up assessments (Days 10, 14, 21, 28, 35, and 42). Acceptable reasons for early discontinuation include the following: 1) non-response to ketamine treatment, 2) request of subject, 3) decision of physician, 4) SAE, 5) and protocol violation.

A subject who decides to discontinue the investigational product will always be asked about the reason(s) and the presence of any AEs. If possible, they will be seen and assessed by an investigator. Adverse events will be followed up (see Section 12.6) until resolution.

If a subject discontinues from the study before randomization to Stage 2, then no further follow-up will be expected. However, if the subject discontinues after randomization, to Stage 2 but before receiving any study treatment, the subject will be asked to return for a final study visit, during which the procedures outlined in the Early Termination Visit procedures will be completed, including AEs and concomitant medication assessments.

If a subject discontinues from the study before completion of Stage 2 and has received at least 1 dose of study drug, the subject will be asked to return for a final study visit, at which the procedures outlined in the Early Termination Visit will be completed. Every effort will be made to follow up with subjects who discontinue from the study prior to Visit 10 (Day 42). If subjects refuse to return to the clinic for the study-related assessments, a modified follow-up through, for example, regular telephone contact or a contact at study closure will be arranged, if agreed to by the subject and in compliance with local data privacy laws/practices. If the subject refuses follow-up, the reason for the refusal and last contact date will be documented in the eCRF and source documents.

Subjects who discontinue from the study will not be replaced.

